5 STUDY OBJECTIVES AND ENDPOINTS

5.1 **Primary Objective and Endpoint**

The primary objective of this study is to evaluate the ability of vadadustat to increase the Hb concentration in subjects with anemia secondary to DD-CKD who are hyporesponsive to ESAs.

The primary endpoint is to evaluate the change in Hb from baseline over time during the treatment period.

5.2 Secondary Objectives and Endpoints

The secondary objectives of this study are to evaluate the safety and efficacy of vadadustat compared to epoetin alfa in subjects with anemia secondary to DD-CKD who are hyporesponsive to ESAs.

Secondary endpoints:

- Proportion of subjects demonstrating incremental increases in Hb from baseline over time during the treatment period
- Proportion of subjects with Hb values within the target range of 10.0-11.0 g/dL during the treatment period
- Proportion of subjects receiving epoetin alfa rescue
- Proportion of subjects receiving RBC transfusion
- Levels of various biomarkers, including CRP, hepcidin, and vascular endothelial growth factor (VEGF)
- Mean weekly dose of intravenous elemental iron
- Maintenance of iron sufficiency (defined as ferritin ≥100 ng/mL and transferrin saturation [TSAT] ≥20%).
- Resource utilization

Safety endpoints in this study include the following:

- Hb >12.0 g/dL, >13.0 g/dL, or >14.0 g/dL
- Hb increase >1.0 g/dL within any 2-week interval or >2.0 g/dL within any 4-week interval
- AEs and SAEs
- Vital sign measurements and clinical laboratory values

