7.6 Subject Completion and Individual Subject Discontinuation

NOTE: The need for rescue therapy does not constitute study completion and are not criteria for subject withdrawal from the study or permanent discontinuation of study drug (vadadustat or epoetin alfa).

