8.3.10 Rescue Therapy Guidelines

Hemoglobin levels will be monitored throughout the study at scheduled visits and can be measured more frequently based on investigator's clinical judgment.

Rescue therapy with RBC transfusion or epoetin alfa are allowed, but not required during the treatment period. The following rescue therapy guidelines are provided to ensure the safety of study subjects and to standardize the use of rescue in the study. In cases of extenuating clinical circumstances, the investigator may elect to dose outside the rescue therapy guidelines to maintain the Hb within the target range. In such cases, the clinical circumstances should be documented in the subject's record.

- RBC transfusion: Investigators should use their investigative site's transfusion guidelines when determining whether to transfuse a study subject. In general, in the event of an acute or severe loss of blood, RBC transfusion should be administered as clinically indicated. In less severe instances but where there may be worsening of anemia or moderate to severe symptoms of anemia, RBC transfusions are permitted based on the investigator's clinical judgment. Study drug (vadadustat or epoetin alfa) may be continued during the RBC transfusion period.
 - Epoetin alfa rescue therapy: Starting at Week 6, subjects in both treatment arms will be allowed (although not required) to have their Hb rescued with epoetin alfa. When possible, a subject on vadadustat should be on maximum dose of vadadustat for 2 weeks prior to epoetin alfa rescue. Epoetin alfa rescue therapy should be administered based on the approved US product label for adult patients with CKD on dialysis.
 - To qualify for epoetin alfa rescue therapy, each of the following conditions must be fulfilled.

NOTE: Epoetin alfa rescue therapy should be stopped when Hb is ≥ 9.0 g/dL.

- The subject has experienced a clinically significant worsening of their anemia or symptoms of anemia (eg, fatigue, weakness, shortness of breath, chest pain, confusion, or dizziness) compared to baseline
- The subject's Hb is confirmed to be <9.0 g/dL
- The Hb level decreased >0.5 g/dL from baseline
- Reducing the risk of alloimmunization or transfusion-related risks or both is a goal
- For the epoetin alfa treatment arm:

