 - In addition to meeting the rescue criteria noted above, dosing and administration of epoetin alfa rescue therapy should be based on the approved label for adult patients with CKD on dialysis.

- For the vadadustat treatment arm:
 - Epoetin alfa rescue may not be considered until the next study visit if a subject's current vadadustat dose can be increased (ie, if the subject's last vadadustat dose increase was at least 4 weeks earlier and the subject is currently receiving a vadadustat dose of 600 mg/day or less, then vadadustat dose can be increased by 1 tablet to maintain Hb within the target range of 10.0-11.0 g/dL).

NOTE: vadadustat must be temporarily interrupted during epoetin alfa rescue therapy. After epoetin alfa rescue therapy is completed, vadadustat should be resumed and adjusted per the dose adjustment guidelines (Section 8.3.5).

A minimum interval must be observed prior to restarting vadadustat after the last dose of rescue medication, and treatment may be resumed 2 days after last dose of epoetin alfa rescue.

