11 DATA ANALYSIS

Data collected throughout the study will be summarized using descriptive statistics and listed in by-subject listings. Continuous variables will be summarized using number of subjects with data, mean, standard deviation, median, minimum, and maximum. For categorical variables, the number and percentage of subjects in each category will be tabulated.

For continuous endpoints (eg, Hb) where change from baseline will be analyzed and multiple pretreatment values are recorded, baseline will be defined as the mean of all qualifying values collected prior to the first dose of study drug. For other continuous endpoints baseline will be defined as the last available value prior to the first dose of study drug.

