11.2 Study Analysis Populations

The following analysis populations will be used in this study:

- Modified-intent-to-treat (MITT) population: All randomized subjects who receive at least 1 dose of study drug starting from baseline (Day 1) visit, have at least one pre-treatment Hb measurement, and at least one post-treatment Hb measurement. Subjects in the MITT population will be analyzed based on their randomized treatment assignment.
- Per-protocol population: All randomized subjects who receive at least 1 dose of study drug starting from baseline (Day 1) visit, have at least one pre-treatment Hb measurement, have at least one post-treatment Hb measurement, have epoetin alfa dose recorded during Week 18 to 20, and did not receive any rescue therapy from Weeks 12 to 20. Subjects in the per-protocol population will be analyzed based on their randomized treatment assignment.
- Safety population will include subjects who received at least 1 dose of study drug. Subjects in the safety population will be analyzed based on the study drug treatment that they received.

Efficacy analyses will utilize the MITT and per-protocol populations. Safety analyses will utilize the safety population.

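### The epoetin alfa rescue and RBC transfusion proportions are also assigned to a per-protocol set that removes subjects because they were rescued

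*Combined protocol and SAP*

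**What the plan says.** Section 5.2 names two separate secondary endpoints: the proportion of subjects given epoetin alfa rescue, and "Proportion of subjects receiving RBC transfusion". The synopsis lists the same two under its efficacy endpoints.

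Section 8.3.10 treats both remedies as rescue: "Rescue therapy with RBC transfusion or epoetin alfa are allowed, but not required during the treatment period". Transfusion is open throughout treatment. Epoetin alfa rescue opens later: "Starting at Week 6, subjects in both treatment arms will be allowed (although not required) to have their Hb rescued with epoetin alfa". Rescue does not end participation. Section 7.6 says that "The need for rescue therapy does not constitute study completion", and Section 11.2 analyses both efficacy sets by randomized arm.

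Section 11.2 uses the MITT and per-protocol populations for efficacy analyses. MITT has no rescue condition. The per-protocol set requires, among other things, that the subject "did not receive any rescue therapy from Weeks 12 to 20" and has an epoetin alfa dose on record for Weeks 18 to 20. Section 11.6 plans descriptive summaries by treatment group for the primary and secondary endpoints, without formal tests. Neither section exempts the rescue endpoints from the per-protocol set.

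**The concern.** A per-protocol set that drops rescued subjects is a reasonable lens for hemoglobin, where rescue obscures the effect of the assigned drug. It is not a reasonable lens for rescue itself: the event being counted is then also a ground for removing the subject from the count. A reader who meets a per-protocol rescue or transfusion percentage beside the MITT one may take it for the rate among adherent subjects, when part of the difference comes only from the definition of the set.

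What is at stake is the reading of two secondary lines in a descriptive study. No test, decision rule or sample size depends on them.

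**Working it through.** **Inputs**

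| Item | Value | Source |
|---|---|---|
| Treatment period | Day 1 to Week 20 (20 weeks) | Section 6.1 |
| Epoetin rescue window | Week 6 to Week 20 (14 weeks) | Section 8.3.10 |
| Transfusion window | whole treatment period (20 weeks) | Section 8.3.10 |
| Per-protocol rescue exclusion | Weeks 12 to 20 (8 weeks) | Section 11.2 |
| Planned size | 25 per arm | Section 11.1 |
| Rescue and transfusion rates, timing | not given | – |

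The plan states no figure on this point, so there is none to reproduce.

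**Step 1: share of each window removed by definition.** Epoetin rescue: 8/14 = 57%. Transfusion: 8/20 = 40%. Only epoetin rescue in Weeks 6 to 12 and transfusion before Week 12 can still be counted, and only in subjects with no later rescue of either kind.

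**Step 2: one remedy taken alone.** Let p be the MITT proportion with the event and f the share of events falling before Week 12, with one event per subject. Of all subjects, p·f are early cases and stay, while p·(1−f) are late cases and leave. The per-protocol proportion is then

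p·f / (1 − p·(1−f)).

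If all events are early (f = 1) this equals p, so there is no distortion. If all are late (f = 0) it is 0. These are the limits.

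Between them, assume events spread evenly over the window: f = 6/14 for epoetin and 12/20 for transfusion. With p = 20%, epoetin gives 0.0857/0.8857 = 9.7% and transfusion gives 0.12/0.92 = 13.0%. Other assumed rates:

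| Assumed MITT proportion | Epoetin rescue, per-protocol | Transfusion, per-protocol |
|---|---|---|
| 10% | 4.5% | 6.25% |
| 20% | 9.7% | 13.0% |
| 30% | 15.5% | 20.5% |
| 40% | 22.2% | 28.6% |

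This isolates the rescue exclusion and takes every other per-protocol condition as met.

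**Step 3: the two remedies together.** Late rescue of one kind also removes subjects who are non-cases for the other, so the shift need not be downward for both. Assume 3 of 25 transfused, all before Week 12, and 5 different subjects given epoetin rescue, all in Weeks 12 to 20. The set shrinks to 25 − 5 = 20. Transfusion reads 3/20 = 15% against 3/25 = 12% in MITT; epoetin rescue reads 0/20 = 0% against 5/25 = 20%. Neither per-protocol figure is a rescue rate.

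**Step 4: where these illustrations apply.** The Weeks 18 to 20 epoetin-dose condition is plausible for epoetin-arm subjects still on treatment. Vadadustat subjects stop epoetin on Day 1 (Section 8.3.5), and rescue in Weeks 12 to 20 already disqualifies them. Read as an on-treatment requirement, the condition leaves their per-protocol set nearly empty. It would not if a zero dose counts as recorded, or if the first dose on resuming epoetin at Week 20 (Section 8.3.8) counts; the plan does not say. Steps 2 and 3 are therefore not predictions for the vadadustat arm.

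**The case against.** The strongest reply is that little is lost. MITT carries both proportions without any rescue exclusion and will sit beside any per-protocol figure; the exclusion is visible in the definition; and nothing is tested. A sensible programmer might omit rescue rows from per-protocol tables unprompted. With 25 per arm, sampling error is also wide: 5/25 = 20% has an exact 95% interval of 6.8% to 40.7%. All of this stands and sets the severity. It does not remove the point, because the text as written calls for the two per-protocol rows and they have no useful interpretation.

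A reader might go further and infer that the plan errs by having no row for subjects who needed either remedy, and that such a row would give the share who could not be managed on vadadustat alone. The documents do not support this. Both components are prespecified and uncut in MITT, and the overlap can be counted because Section 11 says "Data collected throughout the study will be summarized using descriptive statistics and listed in by-subject listings". Amendment 1 (Appendix B) ties its single-agent rationale to raising hemoglobin, which is the primary endpoint. Nor would the combined row measure failure on vadadustat alone. It would include transfusions for acute blood loss (Section 8.3.10) and miss subjects who stop vadadustat and resume an ESA outside the rescue rules (Sections 8.3.5 and 8.4.2); Section 11.4 already summarises those discontinuations with reasons.

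A reader might also infer that epoetin rescue hides transfusions that would otherwise occur, since one rescue condition is that "Reducing the risk of alloimmunization or transfusion-related risks or both is a goal". That shows intent only. The documents give no figure for transfusions averted, and in an ESA-hyporesponsive population it could be near zero.

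**Conclusion.** The point holds in a narrow form. As written, the plan produces per-protocol proportions for epoetin rescue and transfusion that are selected on their own outcome. The removed share of the window, 57% for epoetin rescue and 40% for transfusion, follows from the text, taking treatment to end at Week 20. The effect in percentage points rests on assumed rates and timing, and runs from no change to the loss of every event; one line can even rise when late use of the other remedy shrinks the denominator.

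It would be wrong to infer that per-protocol rescue must be zero, since events before Week 12 can remain, or that the MITT results are compromised, since they are not. Severity is minor: the study is descriptive and the primary hemoglobin endpoint is not touched by this point.

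**What to change.** In Sections 11.2 and 11.6, state that the epoetin alfa rescue and RBC transfusion proportions are summarised by arm with 95% confidence intervals in the MITT population only, from Day 1 to Week 20, and are not presented in the per-protocol set. Naming the window matters because Section 9.4.5 still reviews rescue use at Week 24.

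A row for either remedy in MITT may be added as an optional description. It is not a correction and should not be labelled as the share who could not be managed on vadadustat alone.

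The cost is a sentence in each section and two fewer per-protocol rows. Both remedies are already recorded (Section 8.4.3) and reviewed from Day 1 (Appendix A), so data collection, rescue rules and sample size stay as they are.

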6 STUDY DESIGN

[figure not shown]
6.1 Study Design

This is a Phase 2, randomized, open-label study to evaluate vadadustat for the treatment of anemia in subjects with DD-CKD who are hyporesponsive to ESAs. Approximately 50 subjects (n=25 subjects per treatment arm) will be enrolled at approximately 35 investigative sites in the United States.

The study population will consist of subjects with DD-CKD who are ≥ 18 years of age, receiving chronic, maintenance, in-center hemodialysis on an outpatient basis (3 times per week) for end-stage renal disease and for at least 6 months prior to screening, and are hyporesponsive to ESAs

As presented in Figure 2, the study includes a screening period (up to 28 days; Week-4 to Day-4), a study treatment period (from Day 1 to Week 20), and a safety follow-up period (Week 20-24). Therefore, individual eligible subjects will participate in the study for up to 28 weeks. Additional information about each of these study periods is provided below, and clinical and safety assessments will be performed as indicated in Appendix A.

Figure 2 Schematic of the Study Design

Screening Period (Week -4 to Day -4):

The screening period starts at the time the informed consent is signed and will be a maximum of 28 days in duration. The baseline visit on Day 1 will be performed within 28 days of the start of screening and a minimum of 4 days must elapse between the last screening visit and the baseline visit.

Subjects who meet all inclusion and none of the exclusion criteria will be randomly allocated (1:1 ratio) using the interactive web response (IWR) system to participate in either the vadadustat or epoetin alfa treatment arm. Permuted block randomization will be used to assign subjects to treatment.

Study Treatment Period (Baseline [Day 1] to Week 20):

Study drug treatment will aim to maintain Hb level within target range of 10.0 to 11.0 g/dL.

- Vadadustat treatment arm: Subjects who are randomized to the vadadustat treatment arm will discontinue epoetin and will initiate vadadustat dosing at a on Day 1. Additional information on vadadustat dosing adjustments is provided in Section 8.3.5.
- **Epoetin alfa treatment arm**: Subjects who are randomized to the epoetin alfa treatment arm will continue to receive epoetin alfa at the same dose that they were receiving during the screening period. Epoetin alfa dose can be titrated as clinically indicated; and additional information is provided in Section 8.3.4.

Safety Follow-Up Period (Weeks 20 to 24):

The 4-week safety follow-up period starting at Week 20 will be followed by a post-treatment safety assessment conducted at Week 24.

Internal Safety Assessment

An internal Safety Monitoring Committee (SMC) will review safety data on a regular basis, throughout the course of the study. The details of the SMC will be outlined in a study-specific safety monitoring plan.

6.2 Rationale for Study Design

The primary objective of this study is to evaluate the ability of vadadustat to increase the Hb concentration in subjects with anemia secondary to DD-CKD who are hyporesponsive to ESAs. In this study, epoetin alfa has been chosen as an active comparator as it is marketed and available globally, has an extensive safety profile, and has been the standard of care in many hemodialysis centers, including DaVita dialysis centers in the US. Since the study will be conducted mostly at DaVita dialysis centers in the US, a single active comparator epoetin alfa has been selected, thereby reducing variability and simplifying trial logistics.

In a previous study (AKB-6548-CI-0011), subjects with DD-CKD who were directly switched from ESA to vadadustat achieved stable levels of Hb over 16 weeks. This study also demonstrated improvement of iron mobilization, as reflected by increases in TIBC and serum iron, and decreases in serum ferritin and hepcidin levels.

The present study is to apply a similar design to switch subjects from their current dose of ESA to vadadustat. Subjects who are randomized to the direct switching arm will have an initial vadadustat dose of **Sector**, with the flexibility of increasing or decreasing the dose level based on Hb response, which will be closely monitored throughout the study.

The study design also includes a comprehensive vadadustat dose adjustment guideline and epoetin alfa rescue algorithm to ensure Hb can be maintained within the target range of 10.0-11.0 g/dL (see Sections 8.3.5 and 8.3.10).

6.3 Dose Justification

To date, vadadustat has been evaluated in patients with DD-CKD and NDD-CKD. In the present Phase 2, open-label, study of ESA hyporesponsive subjects, an initial dose of along with a dose range of the study of the

In the ongoing, global, Phase 3 open-label, randomized trial evaluating vadadustat versus darbepoetin alfa in subjects with DD-CKD (INNO₂VATE-Conversion; ClinicalTrials.gov Identifier: NCT02892149),

Vadadustat demonstrated dose-proportional PK and achieved serum EPO concentrations that are considered physiologic and below exposures achieved with injectable ESAs. A higher incidence of gastrointestinal AEs (e.g., nausea, diarrhea, abdominal pain) was observed in groups treated with the server and the server with the server with the server and the server with the server and the server action of the server and the server

In addition, the mean anticipated maximum concentration observed (C_{max})and area under the curve (AUC) at steady state for the 750 mg once daily dose are expected to be approximately 20% higher than those seen with the 600 mg once daily dose, previously tested in DD-CKD and NDD-CKD patient populations.

A vadadustat dosing algorithm designed to maintain Hb in a predictable and controlled manner while minimizing abrupt increases or excessive rises in Hb levels is being utilized in the global Phase 3 studies. In the present study, frequent Hb monitoring and use of the vadadustat dosing algorithm will be implemented to mitigate the potential risk of a rapid Hb rise. Furthermore, the protocol specifies that phlebotomy may be considered in the setting of high Hb levels (>14 g/dL) or a high Hb rate of rise, based on the Investigator's judgment. Lastly, the Phase 2b NDD-CKD study (CI-0007) demonstrated that cessation of treatment resulted in prompt reduction in mean Hb to baseline values.

Given that vadadustat only results in physiologic increases in erythropoietin—as opposed to pharmacologic increases following administration of recombinant ESAs—it is anticipated that the beneficial effect of HIF stabilization with vadadustat will be related to improvements in iron mobilization to the bone marrow and promotion of erythropoiesis, if observed in this ESA hyporesponsive patient population. Conversely, to minimize the possibility for sudden declines in Hb in the vadadustat treatment arm, frequent Hb monitoring, and guidance for rescue therapy (Epoetin Alfa Rescue Therapy and/or Red Blood cell transfusions) are provided.

7 SELECTION AND WITHDRAWAL OF SUBJECTS

7.1 General Criteria

To be eligible for this study, a subject (or their legally acceptable representative) must provide valid informed consent and must meet the following criteria. Study procedures (including screening tests) may not be performed until after the informed consent has been legally signed.

7.2 Inclusion Criteria

Subjects must meet all the following inclusion criteria to be eligible for study participation:

- 1. ≥ 18 years of age
- 2. Receiving chronic maintenance in-center hemodialysis (3 times per week) for end-stage renal disease for at least 6 months prior to screening
- 3. Currently receiving epoetin alfa for anemia
- 4. Two Hb measurements (by central lab analysis) between 8.5 and 10 g/dL during screening
- 5. Administered intravenous supplemental iron per investigative site's protocol to maintain serum ferritin \geq 100 ng/mL and TSAT \geq 20%
- 6. Folate and vitamin B12 measurements \geq lower limit of normal during screening
- 7. Having dialysis adequacy as indicated by k- dialyzer clearance of urea, t- dialysis time, V-volume of distribution of urea (Kt/V) >1.2
- 8. Understands the procedures and requirements of the study, willing and able to comply with all study procedures, and provides written informed consent and authorization for protected health information disclosure

